9.4. Key Elements of Analysis Plan

All hypothesis tests and confidence intervals will be two-sided. Except where otherwise stated, the estimation of treatment effect will be adjusted for the effects of centre, type of baseline controller (ICS alone vs. ICS/LABA), gender, and age. Centre, as the unit of randomization, will be treated as a random effect.

All efficacy measures over the course of the study will be presented and summarised in graphs and tables. Continuous data will be summarised by means, standard deviations, medians, minimum and maximum; categorical data will be summarised by counts and percentages.

All outcomes will be pertained to the individual participant's level and the analysis model will be adjusted for the effect of centre (cluster).

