9.4.2. Secondary Analyses

All secondary endpoints will be confined to the ITT population.

Continuous efficacy endpoints will be analyzed using analysis of covariance (ANCOVA) and adjusted for centre as a random effect. For daytime and night-time symptom score, the same method (ANCOVA adjusted by centre) will be used if the parametric model assumptions hold. The assumptions of normality and homogeneity of variance will be assessed by inspection of normal probability plots and residual plots. If these assumptions are not met, alternative methods (e.g., nonparametric methods) may be performed in order to assess the robustness of the conclusions from the primary analysis.

For time to event endpoint, stratified log-rank test and Cox regression analysis will be performed with centre, type of baseline controller (ICS alone vs. ICS/LABA), gender and age as the stratification factors. Kaplan-Meier methodology will be used to estimate median time for each treatment arm. Kaplan-Meier curves will be constructed to provide a visual description of the difference between the two treatment arms.

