2. SUMMARY OF KEY PROTOCOL INFORMATION

2.1. Changes to the Protocol Defined Statistical Analysis Plan

There were no changes or deviations to the originally planned statistical analysis specified in the protocol, dated 27-Jun-2016. Some sensitivity and supportive analyses are added in the primary efficacy analysis in this RAP (See details in Section 7.1.3).

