5.3. Multicentre Studies

In this cluster-randomization design, each study centre, considered as a cluster, will be randomized to either ACT guided treatment group or control group (usual care group). The randomization will be stratified according to the hospital level (Tier 3 vs. Tier 2). The hospital level is determined in accordance with the uniform requirements of the government. A Tier 3 hospital is on a larger scale and provides superior medical care than a Tier 2 hospital. Centre, as the unit of randomization, will be treated as a random effect in generalized linear mixed model (GLMM) used to analyse primary endpoints.

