7. EFFICACY ANALYSES

All hypothesis tests and confidence intervals will be two-sided. All efficacy measures over the course of the study will be presented and summarised. Continuous data will be summarised by means, standard deviations (SD), medians, minimum and maximum; categorical data will be summarised by counts and percentages.

All outcomes will be pertained to the individual participant's level and the analysis model will be adjusted for the effect of centre (cluster).

Unless otherwise specified, endpoints / variables defined in Section [7.1](#) and Section [7.2](#) will be summarised using descriptive statistics, graphically presented (where appropriate) and listed.

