For time to event endpoint, Cox regression analysis will be performed with treatment, baseline ACT total score, centre, type of baseline controller (ICS alone vs. ICS/LABA), gender and age as the adjusted factors. The results will be presented as hazard ratio (SE), 95% confidence interval and P-value. Log-rank test and Kaplan-Meier methodology will be used to estimate median time for each treatment arm. Kaplan-Meier curves will be constructed to provide a visual description of the difference between the two treatment arms.

The example SAS codes are as below:

```

proc phreg data=input_data;
class rndgrp actbl invsite blcontrol gender;
model timetol*eventflag(0)= rndgrp actbl invsite blcontrol gender age /
risklimits ties=exact;
hazardratio rndgrp/ diff=all;
run;

proc lifetest data=input_data outsurv=survest;
time timetol*eventflag(0);
strata rndgrp;
run;

```

where `input_data` is the name of the input dataset, `timetol` is the variable for time to response and `eventflag` is the variable for sensor. In terms of the covariates `rndgrp`, `actbl`, `invsite`, `blcontrol`, `gender` and `age` are variables for randomised treatment code, baseline ACT total score, centre, type of baseline controller, gender and age respectively.

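### The Cox model for time to asthma control enters arm and centre together as fixed effects, so the treatment hazard ratio is not identified; the protocol's centre-stratified version carries no treatment information

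*SAP*

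**What the plan says.** SAP 5.3 sets the design: "each study centre, considered as a cluster, will be randomized to either ACT guided treatment group or control group". No centre contains both arms.

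For the two time-to-control endpoints listed in SAP 7.2.1, SAP 7.2.2 says "Cox regression analysis will be performed with treatment, baseline ACT total score, centre, type of baseline controller", gender and age are adjusted for. A hazard ratio with its SE, interval and p-value is to be reported. The prose does not say whether centre is fixed or random. The example code does: `rndgrp` and `invsite` are both CLASS variables, the model line is "model timetol*eventflag(0)= rndgrp actbl invsite blcontrol gender age", and there is no RANDOM statement and no robust-variance option. The LIFETEST step for the log-rank test and Kaplan-Meier curves is grouped by arm only.

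Protocol 9.4.2 has a different method: "stratified log-rank test and Cox regression analysis will be performed with centre, type of baseline controller", gender and age serving as stratification factors. The general rule in Protocol 9.4 is "Centre, as the unit of randomization, will be treated as a random effect", in a paragraph that allows exceptions stated elsewhere. SAP 2.1 nevertheless reports: "There were no changes or deviations to the originally planned statistical analysis specified in the protocol".

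**The concern.** A regression can separate the effect of treatment from the effect of centre only if treatment varies within centres or centre effects are given a distribution. Here neither holds. With centre fixed, the centre terms absorb the whole arm difference. With centre as a stratum, every comparison is made inside a group that has one arm.

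At stake are the hazard ratio, interval and p-value for two listed secondary endpoints. A programmer who followed the code would either get no treatment estimate or get a number set by which centres happen to be the reference levels. That number could be reported as a treatment effect without anyone noticing.

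**Working it through.** **Inputs.** 12 centres, six per arm, about 44 subjects each, 528 in total (Protocol 4.3). Rates 29% and 44%, ICC 0.01, 35 evaluable subjects per centre, 80% power, two-sided 0.05 (Protocol 9.2.1). Six post-baseline ACT visits (Protocol 7.1). The plan gives no power or event figure for time to control, so the ICC is borrowed from the binary endpoint as an assumption.

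**1. The plan's own figure.** Design effect = 1 + (35 − 1) × 0.01 = 1.34. Effective n per arm = 6 × 35 / 1.34 = 156.7. Power = Φ(0.15 / √[(0.29 × 0.71 + 0.44 × 0.56) / 156.7] − 1.96) = 79.7% (79.0% with pooled variance). The stated 80% reproduces, so the ICC and cluster sizes are read correctly.

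**2. SAP model.** The arm indicator equals the sum of the six ACT-centre indicators. Arm (1 column) plus centre (11 columns) makes 12 columns; after centring the rank is 11. The lost dimension is the arm contrast. One illustrative simulated data set (12 × 35, HR 1.5, centre SD 0.1 on the log-hazard scale) shows the effect:

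- The maximised log-likelihood is −877.735872 with or without the treatment term.
- Six choices of reference-centre pair give treatment hazard ratios of 0.98, 1.74, 2.11, 2.04, 2.86 and 1.08, all with that same log-likelihood.
- With centre removed, the estimate is 1.66.

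**3. Protocol model.** Within a centre stratum the arm indicator is constant, so each subject's deviation from the risk-set mean is zero. Score and information are therefore zero. In the same data the stratified log-likelihood is −508.908799 for every log hazard ratio tried from −2 to 2, and the stratified log-rank test has O − E = 0 and variance 0.

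**4. Size of a printed contrast under the SAP code.** Simulation of 12 × 44 subjects: six visits, constant hazard, normal centre effects, no dropout, no other covariates, grouped-time proportional hazards model, 600 to 1,500 replicates per setting. True HR = ln(1 − p₁)/ln(1 − p₀). The ICC was converted to a log-hazard SD by √(ICC·p(1 − p)) / [(1 − p)(−ln(1 − p))], averaged over arms; at 29% and 44% this gives 0.170. The first endpoint also counts an improvement of more than 3 points, so its event rate may be higher; hence the other rows. ICC is 0.01 throughout.

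| Week 24 rates (HR) | SD of log HR, single contrast | SD, no centre term | 95% of printed HRs | Median lowest and highest of the 36 centre pairs |
|---|---|---|---|---|
| 29% vs 44% (1.69) | 0.44–0.46 | 0.17 | 0.73–4.32 | 0.79, 3.85 |
| 45% vs 60% (1.53) | not given | not given | not given | 0.80, 2.92 |
| 60% vs 75% (1.51) | 0.32–0.33 | 0.13 | 0.79–2.90 | 0.86, 2.72 |

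At 29% vs 44% the contrast is centred on the truth (mean log HR 0.54 to 0.56 against 0.53) but very imprecise. Most of the spread is small-centre sampling noise: with ICC 0 the lowest and highest are still 0.89 and 3.34. Read as a treatment test, the contrast has a type I error of 9–11% at ICC 0.01 and 21–30% at ICC 0.05.

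**5. Arm-only log-rank test.** The approximation 2[1 − Φ(1.96/√DE)] gives 9.0% for DE 1.34. For 44 per centre, DE = 1 + 43 × 0.01 = 1.43 and the result is 10.1%. Null simulations (2,500 replicates, common rate 29% to 67.5%) gave:

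- ICC 0: 4.4–5.4%
- ICC 0.01: 8.4–9.4% (35 per centre) and 9.7–10.4% (44 per centre); repeats gave 8.8% to 11.4%
- ICC 0.05: 26–28% (44 per centre); a repeat with 35 per centre gave 23%

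**6. Candidate replacements, type I error.** Centre-robust variance: 9–11% uncorrected, 6–7% with t on 10 df, 4.3–5.3% with the SE also multiplied by √(12/10). Lognormal centre frailty with t on 10 df: 3.6–4.1% at ICC 0.01 and 6.2–6.8% at ICC 0.05.

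**The case against.** The strongest defence is that the code is labelled an example and the intent to adjust for clustering is clear from SAP 7, so centre could be meant as random. The SAP's own contrast tells against this. For the diary, FEV1 and AQLQ(S) models, SAP 7.2.2 calls centre a random factor, codes it so, and lists `invsite` under the random effect. For the Cox model all three are absent and `invsite` is listed as a covariate.

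Some narrower points stand:

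- The random-effect rule in Protocol 9.4 yields where another section says otherwise, and Protocol 9.4.2 does. The clear conflict is between Protocol 9.4.2 and SAP 7.2.2, with SAP 2.1 declaring no change.
- Protocol 9.3 leaves the full analysis description to the SAP, so the stratified version is an inconsistency to reconcile rather than the analysis that would be run. It does mean that falling back on the protocol is no remedy.
- SAP 7.2.2 mentions the log-rank test alongside median times and attaches the p-value to the Cox model. The inflated error matters only if the log-rank result is used as inference.
- The documents do not show what the software would print. The rank result does not depend on this; the spread in step 4 does.
- The frailty results come from a grouped-time model, and its error exceeds 5% at ICC 0.05, so the frailty is the weaker of the two replacements.

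**Conclusion.** The concern holds and should be fixed. As coded, the SAP's Cox model cannot identify the treatment hazard ratio, and the protocol's centre-stratified log-rank and Cox analyses contain no information on treatment. Both results are algebraic. They follow from whole-centre randomisation and do not depend on event rates, ICC or tie handling.

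The sizes do rest on the stated simulation assumptions and the borrowed ICC. A printed value would in effect compare 88 of 528 subjects (2 × 44), with the other centres contributing only through the shared baseline hazard. Its log HR has roughly 2.5 times the SD of an analysis with no centre term.

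The damage is limited to the Cox output for the two time-to-control endpoints, plus the log-rank p-value if it is used. The Kaplan-Meier curves stand as description. The primary model has centre as a random intercept and is unaffected. SAP 5.5 places these endpoints outside any multiplicity scheme, so the trial's main conclusion does not turn on them.

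**What to change.** In both documents, remove centre from the Cox fixed effects and from the strata. Then choose one model:

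- Preferred: a marginal Cox model with centre-level robust variance, SE multiplied by √(12/10), and t on 10 df.
- Alternative: a Cox model with centre as a shared frailty and t on 10 df.

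Name a tie method that the chosen model supports; the present code asks for exact ties, and with ACT read at only six visits ties will be heavy. Hospital tier may be a stratum if both arms occur in each tier. Base the time-to-control p-value on the chosen model, keep Kaplan-Meier as description, and record the change in SAP 2.1 before database lock. For the same reason, delete treatment by centre as the example interaction in Protocol 9.4.3 and SAP 7.1.2, since no centre has both arms.

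The cost is wording, a few lines of code, and an interval wider than one that ignores centre. At ICC 0.01 and 29% vs 44%, the half-width on the log HR is 0.38 (marginal) or 0.35 (frailty), against a nominal 0.29 ignoring centre. That last figure is too narrow: the simulated SD implies 1.96 × 0.17 = 0.33. At 60% vs 75% the three are 0.28, 0.26 and 0.21. The single-centre-pair contrast has a nominal 0.71 that omits between-centre variance; its simulated SD implies 1.96 × 0.44 to 0.46, or 0.86 to 0.90.

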7.3. Efficacy

7.3.1. Primary Endpoint (s)

- The primary endpoint for the study is the percentage of subjects who have an ACT score ≥ 20 or an improvement of more than 3 points in ACT during the 24-week treatment period.

Asthma control test (ACT)

ACT is a self-administered questionnaire comprising five questions [Nathan, 2004]. Each of the five items in the ACT is assessed on a five point scale and the scores are summed

to give a total score ranging from 5 to 25, with a score of ≥ 20 denoting 'well-controlled asthma', a score of 16-19 denoting 'not well-controlled asthma', and a score of ≤ 15 denoting 'very poorly controlled asthma'. The recall period of the questionnaire is four weeks. ACT must be completed by the subject at each visit. For the control group, subjects should complete the ACT after investigator making the treatment decision. Differences of 3 points in mean ACT scores between 2 groups or over time in an individual patient are clinically significant [Schatz, 2009]. An improvement of more than 3 points in ACT from baseline will also serve as primary endpoint.

The questionnaire will be attached separately.

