9.2. Sample Size Considerations

9.2.1. Sample Size Assumptions

The study will be powered to demonstrate superiority of ACT guided treatment over usual care from baseline over Week 24 in the primary endpoints.

We assume an intra-cluster correlation coefficient (ICC) of $\rho=0.01$, 29% well-control rate for usual care group, and 44% for ACT guided treatment group. It is required to have 6 centres for each treatment group and a minimum of 35 subjects for each centre (a total of 420 evaluable subjects) to achieve a power of 80% with two-sided $\alpha=0.05$. We anticipate a dropout rate of 20% and therefore planned to recruit 44 subjects in each centre (a total of 528 randomized subjects). These sample size calculations are produced based on Donner [[Donner, 1981](#)].

An ACT score ≥ 20 indicates controlled asthma. The assumed rate of subjects with an ACT score ≥ 20 for usual care group is based on a nationwide epidemiologic survey in

China [Nan, 2013], which reported a 29% asthma control rate. The rate for ACT guided treatment is assumed based on GOAL study [Bateman, 2004], which reported a 80% rate for salmeterol/fluticasone group. An additional adjustment has been made to reduce it to 44% to account for real life practice. A 15% difference between ACT guided treatment group and usual care group is considered clinically meaningful.

Study centres will be randomly assigned to the 2 groups using a computer generated randomization list. The randomization will be stratified according to the Tier of the hospitals (Tier 3 vs. Tier 2).

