5. CONSIDERATIONS FOR DATA ANALYSES AND DATA HANDLING CONVENTIONS

Continuous data will be summarized by treatment using descriptive statistics: number of subjects/observations (n), arithmetic mean values (Mean), median value (Median), standard deviation (SD), minimum value (Min), and maximum value (Max). Min and Max will be presented with the same number of decimal places as the raw data recorded in the database. Mean and Median will be presented using one more additional decimal place. SD will be presented with two more decimal places than the raw data recorded in the database.

Categorical data will be summarized by treatment using frequencies and percentages. Counts and percentages will be presented for each category. Percentages will be presented to one decimal place.

Statistical tests of treatment effects will be performed at a 2-sided significance level of 0.05, unless otherwise stated. And all p-values will be rounded up to 3 decimal places.

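### First ACT response is seen only at 4-weekly visits, yet the SAP leaves the time variable undefined; if it holds visit dates, centre booking habits cannot be separated from treatment

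*SAP*

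**What the plan says.** Protocol 4.2 has ACT completed in clinic at Weeks 4, 8, 12, 16, 20 and 24. The Time and Events Table (Protocol 7.1, repeated in SAP 10.2.1) gives each visit a ±1 window, which I read as ±1 week. On the instrument, Protocol 7.3.1 states: "The recall period of the questionnaire is four weeks".

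SAP 7.2.1 lists two time-to-first-response endpoints: ACT at least 20 **or** a gain above 3 points, and the same two conditions joined by **and**. For these, SAP 7.2.2 plans:

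- Cox regression (PROC PHREG, exact tie handling) with centre as a fixed class term;
- a log-rank test and Kaplan-Meier curves (PROC LIFETEST) with arm as the only stratum. The text reads "Log-rank test and Kaplan-Meier methodology will be used to estimate median time for each treatment arm";
- a median time with a 95% confidence interval.

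The variable timetol is described only as time to response. Nothing says whether it counts days or visits, when non-responders are censored, or how a missed visit is treated. Centre is the unit of randomisation (SAP 5.3), and efficacy p-values are not adjusted for multiplicity (SAP 5.5).

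**The concern.** First response is interval-censored: it happened at some point between the last visit without response and the first visit with it. The planned methods take one time per patient as the event time.

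If that time is the visit date, two patients who first respond at the same visit are ranked by when the clinic happened to see them, and those dates can differ by up to 14 days. Suppose one centre tends to see Visit 1 patients on day 26 and another on day 30, with the same proportion responding. Every response at the first centre then counts as faster.

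Under individual randomisation such habits would be spread over both arms. Here a centre's habit lies wholly in one arm, with only six centres per arm. At stake is whether a log-rank p-value or a median in days reflects asthma control or the appointment book.

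**Working it through.** **1. The plan's own figure.** The documents give no event count, median or hazard ratio for this endpoint. The only sizing is for the primary endpoint: "29% well-control rate for usual care group, and 44% for ACT guided treatment group", ICC 0.01, two-sided 5%, 80% power (Protocol 9.2.1).

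- Per arm, unpooled variance: (1.960 + 0.842)² × (0.29×0.71 + 0.44×0.56) / 0.15² = 157.8.
- Design effect: 1 + (35 − 1) × 0.01 = 1.34.
- Total: 157.8 × 1.34 × 2 = 423, against 420 stated.
- Power with 210 / 1.34 = 156.7 effective subjects per arm: 79.0%.
- Dropout: 35 / 0.8 = 43.75, so 44 per centre, and 44 × 12 = 528.

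This reproduces and is not in dispute. It supplies the layout used below: 12 centres of 35.

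**2. Simulation with no treatment effect, log-rank test unadjusted for centre.** There were 1,500 trials per setting, six visits, and dates held within ±7 days of schedule. My assumptions, not in the documents, are a 24-week response of 29%, 44%, 70% or 90%, and response either tied to the visit or crossed at a constant daily hazard between visits. Each cell is the range over the settings in that row. Hazard ratios are log-rank based.

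| Assumed booking | Type I error, actual days | Type I error, visit number |
|---|---|---|
| On the nominal day, or patient-level jitter only | 4.1–5.9% | 4.2–5.9% |
| Centre habits uniform ±5 days, patient jitter ±2 days, no arm pattern | 6.4–10.5% | 4.2–6.7% |
| Arms shifted ±1 day (2-day gap) | 7.1–19.1% (HR 1.08–1.12) | 4.2–6.5% (HR 0.97–1.01) |
| Arms shifted ±3 days, response tied to visit | 24.3–71.5% (HR 1.26–1.31) | 4.8–5.3% (HR 1.00–1.01) |
| Arms shifted ±3 days, continuous crossing | 17.1–42.7% (HR 1.19–1.21) | 5.7–11.3% (HR 0.91–0.95) |

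Simulation error around 5% is 1.96 × √(0.05×0.95/1500) = 1.1 points, so the second row is a real but modest excess.

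**3. A second set of assumptions.** Centre habit SD 2 days, 2,000 trials per setting, cumulative response 40%, 64% or 75%:

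- no arm shift: 5.5%, 6.0% and 9.3%;
- 2-day gap, within-centre SD 1.5 days, centre SD 0 or 2 days, non-responders censored at their actual Visit 6 date: 7–9%, 12–17% and 18–27%.

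**4. How large a gap chance alone produces.** With centre SD 2 days and six centres per arm, the difference in arm means has SD 2 × √(2/6) = 1.15 days. A gap of 2 days or more then has probability of about 8%, and of 4 days or more about 0.05%. Such chance gaps are already averaged into the no-shift figures.

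**5. The median.** If a Kaplan-Meier median is reached it can fall only on a visit date. If cumulative response were the planned 29% and 44%, it would not be reached in either arm. Those rates refer to ACT at least 20 (Protocol 9.2.1). The first endpoint also counts a gain above 3 points at any visit, so its cumulative response may be higher.

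**The case against.** The strongest reply is that the SAP never says time is in days. Study Day is marked not applicable (SAP 10.4.1), and withdrawal visits may be slotted to the schedule (SAP 10.5.1). Both hint at scheduled-visit time, under which the artefact largely disappears. Exact tie handling does not show that times are taken as exactly observed, since it suits heavily tied visit-level data at least as well. This all stands, and it makes the concern conditional. It does not settle the unit, so the SAP must still define it.

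A reader might infer that the analysis will produce a false treatment effect because ACT centres book earlier. The documents do not support that: both arms share one schedule and one window. The large errors in the table come from arm shifts imposed in the simulation.

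Nor can the simulated hazard ratios be read as output of the planned Cox model. Treatment plus 11 centre indicators has rank 11 of 12, so the arm contrast is not estimable there. That is a separate and more serious defect. Ordinary clustering also inflates the unadjusted log-rank test whatever the visit timing (10% to 19% with an assumed between-centre log-hazard SD of 0.2).

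Finally, SAP 7.1.3 already presents response by scheduled visit, so readers could see identical visit-by-visit response.

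**Conclusion.** The point holds in conditional form. First response is interval-censored and the time variable is undefined. If actual visit dates are used, booking habits enter the event times and are confounded with arm.

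Without an arm pattern in booking, type I error is about 5% to 11% for assumed centre habits with SD 2 to 3.5 days or uniform within ±5 days, against 4% to 7% with visit number. It clearly exceeds that range only if booking differs systematically by arm: about 7% to 27% for an assumed 2-day gap, depending on response rate. The documents give no evidence of such a difference. All these sizes rest on assumed booking habits and response rates.

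The endpoints are secondary and the primary analysis is unaffected. This is a cheap improvement.

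**What to change.** In SAP 7.2.2:

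- Define time as scheduled visit number, 1 to 6. State the event visit, the censoring visit for non-responders and withdrawals, which visit an early-withdrawal ACT counts towards, and the rule for a missed visit.
- Replace the Cox and log-rank comparison with a grouped-time model: PROC GLIMMIX, binomial, complementary log-log link, visit as a class factor, the planned covariates, and a random intercept for centre. Report the grouped-time hazard ratio. The random intercept also makes the arm contrast estimable.
- Run Kaplan-Meier on scheduled week, and report the cumulative percentage controlled by each visit in place of a median in days.
- Add an interval-censored sensitivity analysis using the actual dates of the last non-response and first response visits. It is needed because visit-number time can be biased the other way: with arm shifts of ±3 to ±5 days and control arising in continuous time, HR was 0.86 to 0.95 and type I error 6% to 25%.

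The cost is SAP text and code. GLIMMIX is already used for the primary analysis and no new data are needed. The downside is that visit-date information is used only in the sensitivity analysis.
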